Appendix 3. Criteria for Classification of Functional Status in Rheumatoid Arthritis

Class I: Completely able to perform usual activities of daily living (self-care, vocational, and avocational).

Class II: Able to perform usual self-care and vocational activities, but limited in avocational activities.

Class III: Able to perform usual self-care activities, but limited in vocational and avocational activities.

Class IV: Limited in ability to perform usual self-care, vocational, and avocational activities.

Usual self-care activities including dressing, feeding, bathing, grooming, and toileting. Avocational (recreational and/or leisure) and vocational (work, school, homemaking) activities are patient-desired and age- and sex-specific.

Appendix 4. Leflunomide Wash-out Procedures

Leflunomide: Subjects must have discontinued 4 weeks for leflunomide with an elimination procedure as follows: cholestyramine at a dosage of 8 grams 3 times daily for at least 24 hours, or activated charcoal at a dosage of 50 grams 4 times a day for at least 24 hours.

Appendix 5. Prohibited Concomitant Medications

CYP3A4, 5,7 and/or CYP2C19 Inhibitors

delavirdine (Rescriptor)
indinavir (Crixivan)
nelfinavir (Viracept)

ritonavir (Kaletra, Norvir)
saquinavir (Fortovase)

amiodarone (Cordarone, Pacerone)

cimetidine (Tagamet)
ciprofloxacin (Cipro)
clarithromycin (Biaxin, Prevpac)
Telithromycin (Ketek)
chloramphenicol
voriconazole (Vfend)
diethyl-dithiocarbamate
diltiazem (Cardizem, Tiazac)
erythromycin
fluconazole (Diflucan)
fluvoxamine (Luvox)
gestodene (Femodene, Melodene,
Minulette, Mirelle, Triodene ED)
grapefruit juice
itraconazole (Sporanox)
ketoconazole (Nizoral)
mifepristone (Mifeprex, RU486)
nefazodone (Serzone)
norfloxacin (Shibroxin, Noroxin)
norflouxetine
mibefradil
verapamil (Calan SR, Covera HS,
Isoptin SR, Tarka, Verelan)

CYP3A Inducers

efavirenz (Sustiva)
nevirapine (Viramune)
barbiturates
carbamazepine (Carbatrol,
Tegretol)
modafinil (Provigil)
phenobarbital
phenytoin (Dilantin,
Phenytek)
rifampin (Rifadin,
Rifamate, Rifater)
St. John's wort
troglitazone (Rezulin)
pioglitazone (Actos)

rifabutin (Mycobutin)

BCRP Inhibitors

cyclosporine
Elacridar (FG120918)
eltrombopag
gefitinib

Appendix 6. Guidelines for Monitoring and Discontinuations

The following laboratory abnormalities require re-testing within one week:

- neutrophil counts <1000 neutrophils/ mm^3 ,
- a decrease of hemoglobin <2.0 g/dL from baseline, regardless of baseline value,
- platelet counts $<75,000$ platelets/ mm^3 ,
- an increase in serum creatinine of $>30\%$ AND >0.2 mg/dL from baseline.

Treatment with Tofacitinib will be discontinued and the subject withdrawn from this study for:

- serious infections (those requiring parenteral antimicrobial therapy or hospitalization),
- confirmed neutrophil counts <500 neutrophils / mm^3 ,
- confirmed hemoglobin <7.5 g/dL,
- confirmed platelet counts $<50,000$ platelets/ mm^3 ,
- confirmed AST or ALT elevations >3 X ULN which do not resolve promptly with adjustment of concomitant medications,
- confirmed increase in serum creatinine $>50\%$ over baseline value,
- other serious or severe AEs, after consultation with the Pfizer clinician.

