7.7. Triggered Requirements

Condition	Action
Neutrophil counts <1000 cells/mm ³	The subject should return to the study site for prompt retesting, ideally within 3-5 days .
Platelet counts <100,000 platelets/mm ³	The subject should return to the study site for prompt retesting, ideally within 3-5 days .
Lymphocyte counts <500 lymphocytes/mm ³	The subject should return to the study site for prompt retesting, ideally within 3-5 days .
Any single AST and/or ALT elevation >3 times the upper limit of normal (ULN)*	The subject should return to the study site for prompt retesting, ideally within 3-5 days .*
Any single hemoglobin value <8.0 g/dL or one that drops ≥2 g/dL below baseline.	The subject should return to the study site for prompt retesting, ideally within 3-5 days .
Any serum creatinine increase >50% over the average of screening (most recent value prior to baseline) and baseline values OR an absolute increase in serum creatinine >0.3 mg/dL (>26.5 μmol/L) over the average of screening (most recent value prior to baseline) and baseline values	The subject should return to the study site for prompt retesting, ideally within 3-5 days . If the second assessment (after the 1 st observations of ≥0.3 mg/dL (or ≥26.5 μmol/L) in serum creatinine relative to subjects' own baseline measurement) is ≥0.4 mg/dL (or ≥35.4 μmol/L), the subject should be discontinued from the study and adequate, immediate, supportive measures taken to correct apparent acute kidney injury.

* The subject must return to the study site for prompt retesting and include the following tests: albumin, creatine kinase (CK), total bilirubin, direct and indirect bilirubin, GGT, PT/INR, and alkaline phosphatase. Additional investigations include a detailed history, occupational exposure, sexual history, travel history, history of contact with a jaundiced subject, surgery, blood transfusion, history of liver or allergic disease, work exposure, history of ethanol, recreational drug and dietary supplement consumption. Testing for acute hepatitis A, B or C infection and biliary tract imaging may be considered. A subject with a total bilirubin value ≥2 × ULN concurrently may need to return to the investigational site and be evaluated as soon as possible, preferably within 48 hours from awareness of the abnormal results (refer to 8.4.2).

090177e190fc2bd0Approved\Approved On: 27-May-2019 05:59 (GMT)

Condition	Action

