2 sequential AST or ALT elevations ≥ 3 x ULN with a total bilirubin value ≥ 2 x ULN	Treatment with all study drugs will be discontinued and the subject withdrawn from this study.
2 sequential AST or ALT elevations ≥ 3 x ULN with an elevated INR	Treatment with all study drugs will be discontinued and the subject withdrawn from this study.
2 sequential AST or ALT elevations ≥ 3 x ULN accompanied by symptoms consistent with hepatic injury	Treatment with all study drugs will be discontinued and the subject withdrawn from this study.
2 sequential AST or ALT elevations ≥ 5 x ULN, regardless of Total Bilirubin or accompanying symptoms	Treatment with all study drugs will be discontinued and the subject withdrawn from this study.
Two sequential hemoglobin values < 8.0 g/dL or a decrease of more than 30% from baseline value;	Treatment with all study drugs will be discontinued and the subject withdrawn from this study. Follow up to resolution
Two sequential platelet counts $< 75,000$ platelets/mm ³ ;	Treatment with all study drugs will be discontinued and the subject withdrawn from this study. Follow up to resolution
2 sequential neutrophil counts < 1000 cells/mm ³	Treatment with all study drugs will be discontinued and the subject withdrawn from this study. Follow up to resolution
Confirmed lymphocyte counts < 500 lymphocytes/mm ³ by repeat testing	Treatment with all study drugs will be discontinued and the subject withdrawn from this study. Follow up to resolution
Confirmed increases in serum creatinine $> 50\%$ over the average of screening and baseline values and the absolute value of serum creatinine is above upper limit of normal range.	Treatment with all study drugs will be discontinued and the subject withdrawn from this study. Retesting should occur until the serum creatinine is within 10% of the pretreatment value.
Serious infections defined as any infection (viral, bacterial, or fungal) requiring parenteral antimicrobial therapy or hospitalization for treatment, or meeting other criteria that require the infection to be classified as a serious adverse event.	Treatment with all study drugs will be discontinued and the subject withdrawn from this study
Opportunistic infection judged significant by investigator	Treatment with all study drugs will be discontinued and the subject withdrawn from this study

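### Appendix 6 gives laboratory retest and stop triggers that conflict, in both directions, with Protocol Sections 7.6.2 and 7.7, and its stop list names only tofacitinib

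*Protocol*

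**What the plan says.** Protocol Appendix 6 (Guidelines for Monitoring and Discontinuations) has two lists. The retest list begins "The following laboratory abnormalities require re-testing within one week" and includes "a decrease of hemoglobin <2.0 g/dL from baseline, regardless of baseline value". The stop list begins "Treatment with Tofacitinib will be discontinued and the subject withdrawn from this study for" and ends with a discretionary item: "other serious or severe AEs, after consultation with the Pfizer clinician".

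Section 7.7 (Triggered Requirements) covers the same tests for all subjects. Its hemoglobin retest row reads "Any single hemoglobin value <8.0 g/dL or one that drops ≥2 g/dL below baseline". Its hemoglobin, platelet, neutrophil and lymphocyte stop rows carry the action "Treatment with all study drugs will be discontinued and the subject withdrawn from this study. Follow up to resolution". For liver enzymes without other findings, the stop is "2 sequential AST or ALT elevations ≥ 5 x ULN, regardless of Total Bilirubin or accompanying symptoms". The stop for a creatinine rise above 50% carries the further condition "and the absolute value of serum creatinine is above upper limit of normal range".

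Section 7.6.2 adds a creatinine rule: retest at a rise of at least 0.3 mg/dL from the subject's own baseline, and discontinue if the second assessment is at least 0.4 mg/dL. Section 7.7 repeats that stop, and Section 6.3 refers to 7.6.2 for acute renal injury.

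**The concern.** For several tests the protocol states two different values at which a subject must be retested or stopped, and no visible text ranks Appendix 6 against Section 7.7. The only precedence statement is in the amendment summary. It puts 7.6.2 above 7.7 for kidney injury and does not mention Appendix 6.

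The appendix title invites use as a quick reference. A site that used it that way could miss a stop that 7.7 requires, retest later, or take a hemoglobin fall of 2 g/dL or more as not listed for retest. A site that used only 7.6.2 and 7.7 would not act on the stricter Appendix 6 items. Subjects could then be retested or stopped at different values at different sites.

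The tofacitinib wording adds a second difficulty. The trial is double-blind and double-dummy (Section 5.2) and packaging conceals contents from site staff (Section 5.4.1), so staff cannot apply a rule to one arm. In regions without a tofacitinib arm (Section 3), the list read literally covers nobody.

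**Working it through.** **Side-by-side comparison.** Inputs are Appendix 6, Section 7.7 and, for creatinine, Section 7.6.2. Stop values are confirmed or sequential in both lists.

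| Item | Appendix 6 | Sections 7.6.2/7.7 | Looser list |
|---|---|---|---|
| Neutrophil stop (/mm³) | <500 | <1000 | Appendix 6 |
| Platelet stop (/mm³) | <50,000 | <75,000 | Appendix 6 |
| Platelet retest (/mm³) | <75,000 | <100,000 | Appendix 6 |
| Hemoglobin stop (g/dL) | <7.5 | <8.0 or fall >30% | Appendix 6 |
| Lymphocyte stop (/mm³) | none | <500 | Appendix 6 |
| Retest time | within one week | ideally 3-5 days; preferably 48 hours for creatinine (7.6.2) | Appendix 6, against a target |
| AST/ALT stop | >3 x ULN, not resolving promptly after adjusting concomitant drugs | ≥5 x ULN, or ≥3 x ULN with bilirubin ≥2 x ULN, raised INR or symptoms | 7.7 |
| Creatinine stop | >50% over baseline | second rise ≥0.4 mg/dL; or >50% and above ULN | depends on baseline |
| Creatinine retest | >30% and >0.2 mg/dL | rise ≥0.3 mg/dL (7.6.2); >50% or >0.3 mg/dL (7.7) | depends on baseline |

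Two items agree: the neutrophil retest (<1000/mm³) and withdrawal for serious infection.

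**Hemoglobin stop.** With baseline B, 7.7 stops below the larger of 8.0 and 0.7B. The 30% rule takes over when 0.7B > 8.0, that is B > 8.0/0.7 = 11.43 g/dL. Appendix 6 stops only below 7.5.
- B = 12.0: 0.7 x 12.0 = 8.4, so values from 7.5 to <8.4 stop under 7.7 only.
- B = 13.0: 0.7 x 13.0 = 9.1, so values from 7.5 to <9.1 stop under 7.7 only.

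**Hemoglobin retest.** As printed, a fall of 0.5 g/dL triggers Appendix 6 but not the 7.7 drop rule, and a fall of 3.0 g/dL does the opposite.

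**Creatinine stop.** Assume screening = baseline = B, and read the 0.4 mg/dL in 7.6.2 as a rise. 7.6.2/7.7 stop at a rise ≥0.40; Appendix 6 stops at a rise >0.50B. They meet at 0.50B = 0.40, so B = 0.80 mg/dL.
- B = 0.90: 0.50B = 0.45, so rises of 0.40 to 0.45 (values 1.30 to 1.35) stop only under 7.6.2/7.7. Example: 1.32 is +0.42, and 0.42/0.90 = 46.7%.
- B = 0.60: 0.50B = 0.30, so rises >0.30 and <0.40 (values >0.90 and <1.00) stop under Appendix 6. Example: 0.95 is +0.35, and 0.35/0.60 = 58.3%. The visible 7.6.2/7.7 rules do not stop this subject if ULN is at least 0.95 mg/dL. The documents give no ULN. Each other value in the range needs a ULN at or above that value: with ULN 0.95, a value of 0.97 (+0.37, 61.7%) is above ULN, so 7.7 stops it too.

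**Creatinine retest.** Appendix 6 requires a rise above the larger of 0.30B and 0.2. Since 0.30B < 0.3 when B < 1.0, it triggers before the 0.3 mg/dL rule at baselines below 1.0 mg/dL. (Below 0.40 mg/dL the 50% rule in 7.7 would come first, since 0.50B < 0.2.)
- 0.70 to 0.95: +0.25, 35.7%. Appendix 6 retests; 7.6.2 and 7.7 do not.
- 1.10 to 1.42: +0.32, 29.1%. 7.6.2 and 7.7 retest; Appendix 6 does not.

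**The case against.** The strongest reply is that nothing operative conflicts. I found no reference to Appendix 6 in the visible protocol outside the list of appendices. The binding stops are in 6.3, 7.6.2 and 7.7, and 7.7 covers all study drugs. No Appendix 6 line permits continued dosing, so a site can obey every list by taking the stricter action. The appendix also has its own consultation route for serious or severe events. This stands and limits the severity. It does not remove the discrepancy for a site that takes the appendix as its reference.

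Some stronger readings are tempting and are not supported:
- That Appendix 6 overrides 7.7 or lets subjects continue below the 7.7 limits. It says neither.
- That its AST/ALT line is an automatic stop. It depends on a clinical judgement about prompt resolution after changing concomitant medication, and 7.7 already requires retest and work-up above 3 x ULN.
- That the retest intervals are conflicting hard limits. Those in 7.6.2 and 7.7 are targets.
- That the whole low-baseline creatinine gap is stopped only by Appendix 6. That depends on ULN, and text near the renal rules in 6.3 and 7.6.2 is redacted.

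The reversed hemoglobin sign may be a PDF misread. The other discrepancies do not rest on it. An intended tofacitinib-only rule does not explain the list either: sites are blinded, and tofacitinib subjects already fall under 7.7.

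**Conclusion.** Appendix 6 is wrong as written and should be fixed, as a matter of consistency in safety thresholds. It does not show that subjects lack protection under the main text.

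The firm part needs no assumption. Confirmed neutrophils of 500-999/mm³, platelets of 50,000-74,999/mm³, lymphocytes below 500/mm³, and hemoglobin from 7.5 to <8.0 g/dL (wider above a baseline of about 11.4 g/dL) are stops under 7.7, with only the consultation route in Appendix 6. In the other direction, Appendix 6 alone addresses persistent isolated AST/ALT between 3 and 5 x ULN as a possible stop, and retests creatinine earlier at baselines below 1.0 mg/dL. The creatinine stop crossover at 0.80 mg/dL assumes equal screening and baseline values and reads 0.4 mg/dL as a rise; the low-baseline side also depends on ULN.

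That the appendix is a leftover is an inference. It is supported by Amendment 1, which removed tofacitinib from the 7.7 heading so that 7.7 applies to all subjects, while Appendix 6 kept the tofacitinib wording.

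**What to change.** Replace Appendix 6 with a cross-reference to, or an exact copy of, the thresholds and retest intervals in 7.6.2 and 7.7, worded for all blinded study drug.

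Before deleting it, decide and record whether each of these moves into 7.6.2/7.7:
- creatinine retest at >30% and >0.2 mg/dL over baseline;
- withdrawal for confirmed AST/ALT >3 x ULN that does not resolve promptly;
- withdrawal for creatinine >50% over baseline regardless of ULN;
- the consultation route for other serious or severe adverse events.

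The first matters because Amendment 1 added visits to increase renal monitoring; deleting the list without a decision would silently drop an earlier renal trigger. If the list is kept, correct the hemoglobin retest trigger to a drop of at least 2 g/dL.

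Cost: a protocol clarification and a site memo, with no added visits or patients. Adopting the earlier creatinine retest in 7.6.2/7.7 would add no test that Appendix 6 does not already require.

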5.2. Breaking the Blind

This is a double blind, double dummy study. At the initiation of the study, the study site will be instructed on the method for breaking the blind. The method will be either a manual or an electronic process. Blinding codes should be broken only in emergency situations for reasons of subject safety. Whenever possible, the investigator or subinvestigator consults with a member of the study team prior to breaking the blind. When the blinding code is broken, the reason must be fully documented and entered on the case report form (CRF).

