5.4. Investigational Product Supplies

5.4.1. Dosage Form(s) and Packaging

Blinded PF-06650833 and its matched placebo will be provided as MR tablets for oral administration. The 20 mg, 100 mg MR tablets and their matching placebos will be supplied in blisters and labeled according to local regulatory requirements. Tablets are described in

the table below. The abbreviations CR (controlled release) and MR (modified release) tablets are synonymous for this protocol. Tofacitinib citrate tablets described in the table below are immediate release formulations.

Total Daily Dose Dose	Number of Tablets	Packaging
PF-06650833 400 mg, QD	4 x 100 mg PF-06650833 tablets	Blister
PF-06650833 200 mg, QD	2 x 100 mg PF-06650833 + 2 x PF-06650833 placebo tablets	Blister
PF-06650833 60 mg, QD	3 x 20 mg PF-06650833 + 1 PF-06650833 placebo tablets	Blister
PF-06650833 20 mg, QD	1 x 20 mg PF-06650833 + 3 PF-06650833 placebo tablets	Blister
PF-06650833 PBO, QD	4 x PF-06650833 placebo tablets	Blister
Tofacitinib 5 mg, BID	2 x 5 mg tofacitinib tablet	Bottle
Placebo for Tofacitinib 5 mg, BID	2 x tofacitinib placebo tablets	Bottle

When received by the pharmacy, PF-06650833 20 mg, 100 mg and matching placebo tablets and tofacitinib 5 mg or matching placebo tablets will be in containers that will sufficiently blind all site staff to contents.

In regions where tofacitinib's inclusion as an active control in this study is not accepted by local regulatory authorities and ethics committees, subjects will only be randomized to PF-06650833 or matching placebo.

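### Appendix 6 conflicts with the all-arm safety rules in Sections 7.6.2 and 7.7: withdrawal tied to tofacitinib under a blind, a reversed hemoglobin re-test, and a lower ALT/AST withdrawal threshold

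*Protocol*

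**What the plan says.** Protocol Appendix 6 holds two lists. The first names laboratory abnormalities that need re-testing within one week. The second gives withdrawal criteria and begins "Treatment with Tofacitinib will be discontinued and the subject withdrawn from this study for".

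Section 7.7 covers the same ground in a table of conditions and actions. Its withdrawal rows read "Treatment with all study drugs will be discontinued and the subject withdrawn from this study", with no reference to arm. Section 7.6.2 adds the acute kidney injury rule, which Section 7.7 repeats.

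On blinding, Section 5.2 states "This is a double blind, double dummy study" and allows the code to be broken only in safety emergencies. Section 5.4.1 says the tablets "will be in containers that will sufficiently blind all site staff to contents". Section 3 (Table 6) describes regions with no tofacitinib arm.

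Three threshold texts matter most:

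- **Hemoglobin re-test.** Appendix 6 lists a decrease of <2.0 g/dL "from baseline, regardless of baseline value". Section 7.7 lists a value below 8.0 g/dL "or one that drops ≥2 g/dL below baseline".
- **ALT/AST withdrawal.** Appendix 6 lists confirmed elevations above 3 x ULN "which do not resolve promptly with adjustment of concomitant medications". Section 7.7 requires two sequential values of at least 3 x ULN together with high bilirubin, raised INR or symptoms, or two sequential values of at least 5 x ULN "regardless of Total Bilirubin or accompanying symptoms".
- **Creatinine withdrawal.** Appendix 6 lists a confirmed rise above 50%. Section 7.7 lists a confirmed rise above 50% with a value above the ULN. Sections 7.6.2 and 7.7 also discontinue at 0.4 mg/dL or more on a second assessment.

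**The concern.** A mandatory withdrawal rule has to be one the site can apply. A site that cannot see the treatment cannot know whether a tofacitinib-only rule binds a given subject. Read literally, the list covers nobody in regions without that arm. Where the two lists also give different thresholds, two sites can follow the protocol in good faith and act differently on the same laboratory result.

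At stake is consistent safety management. A subject with confirmed, persistent, isolated ALT of 4 x ULN would be withdrawn under Appendix 6 if on tofacitinib. Under Section 7.7 the subject would be re-tested and worked up, and under Section 8.4.2 monitored more often, with no required withdrawal. No visible text says which list governs.

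**Working it through.** No sample size or power figure bears on this point. The check sets the rules side by side and finds the values at which they give different actions.

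**Hemoglobin re-test.** Taking the text as it stands, falls of 0.1 to 1.9 g/dL trigger under Appendix 6 but not under the fall criterion in Section 7.7. Falls of 2.0 to 3.0 g/dL trigger under Section 7.7 but not under Appendix 6. The direction is exactly reversed.

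**ALT/AST.** With normal bilirubin and INR and no symptoms, Section 7.7 withdraws at 5 x ULN or more and Appendix 6 above 3 x ULN if persistent. They disagree for confirmed, persistent values above 3 and below 5 x ULN.

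**Creatinine withdrawal** (mg/dL). Let b be baseline. Assume that screening and baseline values are equal, that the 0.4 in Sections 7.6.2 and 7.7 is a rise from baseline, and that results are reported to 0.01. The documents give no ULN; the range assumed is 0.9 to 1.2.

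- Appendix 6: value above 1.5b.
- Sections 7.6.2/7.7: value of b + 0.4 or more on the second assessment, or above 1.5b if also above the ULN.
- Appendix 6 can be stricter only if 1.5b < b + 0.4, that is b < 0.8.

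| b | Values where only Appendix 6 withdraws |
|---|---|
| 0.5 | 0.76–0.89, for any ULN in the range |
| 0.6 | 0.91–0.99 if ULN ≥1.0; none if 0.9 |
| 0.7 | 1.06–1.09 if ULN ≥1.1; none if ≤1.0 |
| 0.8 | none |

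For b of 0.5 or more the zone is at most 0.4 − 0.5 × 0.5 = 0.15 wide. Above 0.8 the order reverses: at b = 1.0, a confirmed 1.4 (a 40% rise) means discontinuation under Sections 7.6.2/7.7 but not under Appendix 6, which needs more than 1.5.

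**Creatinine re-test.** Appendix 6 triggers at a rise above the larger of 0.3b and 0.2. Sections 7.6.2/7.7 trigger at a rise above 0.5b or of at least 0.3. Appendix 6 is earlier only for b between 0.4 and 1.0:

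| b | Values where only Appendix 6 re-tests |
|---|---|
| 0.5 | 0.71–0.75 |
| 0.6 | 0.81–0.89 |
| 0.7 | 0.92–0.99 |
| 0.8 | 1.05–1.09 |
| 0.9 | 1.18–1.19 |
| 1.0 | none |

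The zone is widest at b = 0.6: 0.30 − 0.20 = 0.10. Above 1.0, Sections 7.6.2/7.7 trigger first; at b = 1.2 they need a rise of 0.3 and Appendix 6 needs more than 0.36.

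If creatinine is reported only to 0.1 mg/dL, the re-test zone is empty. For baselines of 0.4 or more, the withdrawal zone then shrinks to b = 0.4 (value 0.7) and b = 0.5 (value 0.8).

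**Hematology withdrawal limits.** Here Appendix 6 is only looser:

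| Item | Appendix 6 | Section 7.7 |
|---|---|---|
| Neutrophils (/mm³) | <500 | <1000 |
| Platelets (/mm³) | <50,000 | <75,000 |
| Hemoglobin (g/dL) | <7.5 | <8.0 or a fall of more than 30% |
| Lymphocytes (/mm³) | no rule | <500 |

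For hemoglobin, the Section 7.7 limit is the larger of 8.0 and 0.7 × baseline. The crossover is 8.0/0.7 = 11.43 g/dL, so the limit is 8.0 for baselines from the entry minimum of 9.0 up to about 11.4, and 8.4, 9.1 and 9.8 for baselines of 12, 13 and 14. A site that follows Section 7.7 on these items does not breach Appendix 6, so this is misleading rather than contradictory.

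**The case against.** The best defense is that the working rule already exists. Section 7.7 applies whatever the arm and needs no knowledge of treatment. Appendix 6 is titled as guidelines and, apart from the contents list, no readable part of the protocol sends sites to it (some text is redacted). The amendment history records that Section 7.7 was extended to all subjects by dropping tofacitinib from its heading, which suggests that the word in Appendix 6 is a leftover. A cautious site could treat everyone as possibly on tofacitinib, and Section 6.3 lets the investigator or sponsor withdraw any subject for safety.

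Most of this stands, and it limits the harm. It does not remove the conflict. The history does not say which list governs, and discretion to withdraw is not the same as one mandatory rule.

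The defense also defeats three stronger readings that a reader might infer:

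- **Appendix 6 is stricter on creatinine in general.** It is not. The stricter zones are narrow, confined to low baselines, and depend on an unstated ULN. The partly redacted renal item in Section 6.3 may already cover the withdrawal zone.
- **Large hemoglobin falls would go un-retested.** Section 7.7 catches every fall of 2 g/dL or more. The reversed item, taken literally, only adds re-tests after small falls.
- **The conflict unblinds the trial or biases the SDAI comparison.** Nothing in the documents shows either. Under protocol Section 9.2, a withdrawal for an adverse event can change that subject's Week 12 value through baseline carried forward, but no distortion of the PF-06650833 versus placebo comparison follows from the wording. The tofacitinib arm is outside that analysis.

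**Conclusion.** Appendix 6 is wrong as written in three respects: a withdrawal list conditioned on an arm that sites cannot identify, a hemoglobin re-test trigger opposite to Section 7.7, and a mandatory withdrawal for persistent isolated ALT/AST above 3 and below 5 x ULN that Section 7.7 does not require. The creatinine rules are inconsistent in both directions, and the hematology withdrawal limits are merely looser.

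The size is modest. The ALT/AST zone is the one substantive difference in action, and what counts as prompt resolution is not defined. The documents do not allow an estimate of how many subjects would fall in any zone.

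The hemoglobin finding rests on the sign in machine-read text and should be confirmed in the PDF. The creatinine figures rest on the assumptions stated with them.

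**What to change.** Replace both Appendix 6 lists with a reference to Sections 7.6.2 and 7.7, and state that these govern all subjects regardless of arm. This removes the tofacitinib wording, the hemoglobin error and the competing thresholds together.

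Before deletion, the sponsor's clinicians should decide whether they want withdrawal for confirmed, persistent ALT/AST above 3 x ULN. If so, add it to Section 7.7 for all study drugs; the downside is possibly a few more withdrawals. They should also confirm that they accept losing the tighter creatinine triggers at low baselines. The Appendix 6 item on other serious or severe adverse events has no general row in Section 7.7, but Section 6.3 already permits withdrawal for safety.

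The cost is one appendix edit, that clinical decision, and notice to sites through an amendment. Visits, assessments and sample size do not change.
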